### Secondary Hypotheses:

The secondary hypotheses are described below, followed by the statistical tests we plan to utilize.

1. Cesarean delivery rates will not differ between the two groups. This hypothesis will be tested using the Chi-Square or Fisher's exact test. Graphical and statistical methods will be used to show the data descriptively. We will report frequencies and percentages.

2. Maternal outcomes (including but not limited to postpartum hemorrhage, infection, hospital readmission rates, and satisfaction scores) will not differ between the two groups. These hypotheses will be assessed using the Chi-Square or Fisher's exact test for categorical endpoints. For continuous endpoints, a 2-sample t-test or the nonparametric equivalent (Wilcoxon Rank-Sum test) will be used. Graphical and statistical methods will be used to show the data descriptively. For continuous data, we will also report means, medians, standard deviations, and ranges. For categorical data, we will report frequencies and percentages.

3. Fetal outcomes (including but not limited to APGAR scores, umbilical artery pH, and nursery disposition) will not differ between the two groups. These hypotheses will be assessed using the Chi-Square or Fisher's exact test for categorical endpoints. For continuous endpoints, a 2-sample t-test or the nonparametric equivalent (Wilcoxon Rank-Sum test) will be used. Graphical and statistical methods will be used to show the data descriptively. For continuous data, we will also report means, medians, standard deviations, and ranges. For categorical data, we will report frequencies and percentages.

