The use of a Foley catheter for cervical ripening in the outpatient setting has the potential for substantial advancement to the induction process for the patient, provider, and healthcare system. The Foley catheter is a safe, inexpensive method of cervical ripening that causes less fetal heart rate effects than other ripening methods [7, 8]. Women may find gratification by being in their home environment during more of their labor course [12]. Providers and healthcare systems may be better able to allocate their resources with decreased length of stay during the early induction phase. A 2013 Cochrane review of outpatient cervical ripening concluded that more studies are required to demonstrate its efficacy and safety in this setting [5]. Our study will provide additional evidence of safety and efficacy to transition cervical ripening to the outpatient setting.

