### 2.2 Secondary Objective

Our secondary objectives are as follows:

- 1) To compare the cesarean delivery rate among women undergoing outpatient Foley versus inpatient cervical ripening.
- 2) To compare other maternal outcomes including: postpartum hemorrhage, infection, hospital readmission, and satisfaction with the induction process.
- 3) To compare neonatal outcomes including: APGAR scores, umbilical artery pH, and nursery disposition.

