#### B. Enrollment of inpatient comparison (usual care) participants

1. Women who decline participation in the outpatient intervention study may be approached to participate in a limited way as inpatient comparison control participants.
2. The study coordinator will screen the OB White Board daily in the Family Birth Center to identify patients presenting for induction of labor who may be eligible for the study, but not captured during the weekly screening process. Eligible women will be approached, after discussion with their attending obstetric provider, to participate in the study as inpatient comparison usual care participants.
3. Four inpatient comparison control participants will be enrolled with the same parity and BMI strata for every outpatient intervention patient enrolled (see III. A. 3. c. above).

- (a) Patient education and consent
  - (a) The patients will be educated the proposed research study.
  - (b) If the patient elects participation, she will undergo informed consent at that time by a trained research study

coordinator, Principal Investigator, Co-Principal Investigator, or authorized obstetric provider.

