### 3.4 Primary Safety Endpoints

The primary safety outcomes are as follows: heavy vaginal bleeding, severe pain (return to hospital overnight for unrelieved pain), mode of delivery, intrapartum complications (as described above), and fetal outcomes (as described above). These will include overall fetal and maternal survival rates. Based on previous studies, we do not anticipate any difference between safety endpoints in the inpatient vs. outpatient groups.

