## 7.2 Sample Size Determination for Prospective Study

A power analysis was performed and assumed a standard deviation of 8 hours. With 40 subjects in the Foley intervention arm and 160 subjects in the standard of care group, we would have 80% power to detect a  $\frac{1}{2}$  standard deviation reduction in the predelivery hospitalization time from 16 to 12 hours in the standard of care and intervention groups, respectively. This also assumes a 2-sided significance level of 0.05.

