## 7.4 Subject Population(s) for Analysis

We will analyze all subjects who were randomized in the randomized control trial design stage of the study, except those who electively withdrew from the trial. We will analyze all subjects enrolled in the prospective stage of the study, who do not electively withdraw.

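### Secondary outcomes are hypothesized to be the same in both groups, but only difference tests and per-group summaries are planned, with no confidence interval for the difference

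*Combined protocol and SAP*

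**What the plan says.** Section 7.3, Secondary Hypotheses, lists three hypotheses, for cesarean delivery, maternal outcomes and fetal outcomes. Each is worded as an expectation of no difference. The first reads: "Cesarean delivery rates will not differ between the two groups. This hypothesis will be tested using the Chi-Square" (Fisher's exact test is the alternative). The other two use the same tests for categorical endpoints, and a two-sample t-test or Wilcoxon rank-sum test for continuous ones. The Study Summary names the same tests.

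Beyond the tests, Section 7.3 promises counts and percentages for categorical data; means, medians, standard deviations and ranges for continuous data; and unspecified descriptive graphical and statistical methods.

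The objective in Section 2.2 is neutral: "To compare the cesarean delivery rate among women undergoing outpatient Foley versus inpatient cervical ripening". Section 3.4 counts mode of delivery, intrapartum complications and fetal outcomes among the primary safety outcomes and adds that "we do not anticipate any difference between safety endpoints in the inpatient vs. outpatient groups". Section 1.1 states the intended use: "Our study will provide additional evidence of safety and efficacy to transition cervical ripening to the outpatient setting".

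Both sample-size sections (7.1 and 7.2) concern pre-delivery hospitalization time only. For the current design, Section 7.2 begins "With 40 subjects in the Foley intervention arm and 160 subjects in the standard of care group".

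**The concern.** Chi-square, Fisher, t and Wilcoxon tests take equality as the null hypothesis. A small p-value is evidence against equality; a large one may mean that the groups are alike or that the study is too small to tell. The stated hypotheses therefore cannot be supported by the tests assigned to them.

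An interval for the difference would separate those two explanations, but none is planned, and neither is an equivalence or non-inferiority margin or a rule for reading a non-significant result.

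At stake is the safety message. The study is meant to contribute evidence for moving cervical ripening out of hospital, and its outpatient arm has 40 women. A p-value beside two percentages does not state how large an increase in cesarean or neonatal harm the data leave open.

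**Working it through.** **1. The plan's own figure.** Inputs from Section 7.2: 40 versus 160 women, means 12 and 16 hours, SD 8 hours, 80% power ("This also assumes a 2-sided significance level of 0.05").

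- Standardized difference: 4 / (8 × √(1/40 + 1/160)) = 0.5 / 0.1768 = 2.83.
- Power ≈ Φ(2.83 − 1.96) = 80.7%; the noncentral t gives 80.4%.

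The stated 80% reproduces. The arithmetic is sound but covers the primary endpoint alone.

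**2. Assumptions for cesarean delivery.** The documents give neither an inpatient rate nor a difference of concern. I assume rates of 10, 20 and 30% and a true increase of 10 points, and treat the arms as independent. Two-sided alpha of 0.05 is carried over from the primary endpoint, since none is stated for the secondary hypotheses.

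**3. Chance of missing a 10-point increase.** Exact enumeration of Binomial(40) × Binomial(160), chi-square without continuity correction. Fisher power is also by enumeration.

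| Assumed inpatient rate | Chi-square power | Missed, chi-square | Fisher power | Missed, Fisher |
|---|---|---|---|---|
| 10% | 42.3% | 57.7% | 35.7% | 64.3% |
| 20% | 29.2% | 70.8% | 24.9% | 75.1% |
| 30% | 23.9% | 76.1% | 20.5% | 79.5% |

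By the normal approximation, the increase detectable with 80% power is about 18 points at a 10% base rate and 24 points at 30%.

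**4. Precision if the true rates are equal.** The 95% half-width is 1.96 × √(p(1−p)(1/40 + 1/160)):

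- p = 10%: 1.96 × √(0.09 × 0.03125) = 10.4 points
- p = 20%: 1.96 × √(0.16 × 0.03125) = 13.9 points
- p = 30%: 1.96 × √(0.21 × 0.03125) = 15.9 points

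**5. Identical observed rates.** Take 8/40 and 32/160, both 20%; chi-square p = 1.00. The Wilson 95% limits are 10.5 to 34.8% and 14.5 to 26.9%. Newcombe's interval for the difference (outpatient minus inpatient) is:

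- Lower: −√((0.200 − 0.105)² + (0.269 − 0.200)²) = −11.7 points
- Upper: +√((0.348 − 0.200)² + (0.200 − 0.145)²) = +15.7 points

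The planned output would show two equal percentages and p = 1.00; the interval shows that an increase of over 15 points is not excluded.

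**6. No events in the outpatient arm.** With 0/40, the two-sided exact 95% interval reaches 1 − 0.025^(1/40) = 8.8%. The one-sided 95% limit is 1 − 0.05^(1/40) = 7.2%.

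**7. Two sensitivity checks.**

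- *Matching.* Section 3.1 III.B says "Four inpatient comparison control participants will be enrolled with the same parity and BMI strata for every outpatient intervention patient enrolled". I simulated four strata of 10 versus 40 women, 200,000 times, with assumed stratum rates of 4–20%, 8–35% and 15–50% (means 10, 20 and 30%) and 10 points added in each. Missed: 58, 71 and 77% by unstratified chi-square; 57, 70 and 75% by Cochran-Mantel-Haenszel. Independence is an adequate simplification here.
- *Randomized-stage women.* Section 7.4 says "We will analyze all subjects who were randomized in the randomized control trial design stage of the study" but gives no number. With an assumed 20 more per arm (60 versus 180), the increase is missed 47, 63 and 70% of the time.

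**The case against.** The strongest reply is that the inference error is not actually written down. The no-difference wording is paired with tests whose null is no difference, so it may simply be a loosely stated null hypothesis. The objectives are neutral, Section 3.4 expresses an expectation, Section 1.1 promises only further evidence, and nothing says that p > 0.05 will be called equal safety. That stands, and the point does not depend on the stronger reading: on either one, the planned output omits the size of difference left open.

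Second, readers could build approximate intervals from the promised counts, means and SDs. That is true for proportions and means. It is not true for a Hodges-Lehmann shift where Wilcoxon is used, and estimates for primary safety outcomes should not be left to readers.

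Third, low power for secondary endpoints is ordinary, and an interval changes no miss rate. That is also true. The miss rates show why a non-significant result says little; the half-widths and the 8/40 versus 32/160 example measure the gap itself.

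Fourth, the comparison is non-randomized and controls may be women who declined the intervention, so an interval covers sampling error and not confounding. This limit applies equally to the planned unadjusted tests. It is a reason for careful wording, not for omitting the interval.

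**Conclusion.** The point holds. The method assigned to the three secondary hypotheses cannot support them as worded, and no between-group estimate, interval or margin is planned. Across assumed inpatient cesarean rates of 10 to 30%, a true 10-point increase would more likely than not go undetected in the prospective stage (58 to 76% by chi-square), and the 95% half-width for the difference would be about 10 to 16 points. These figures rest on assumed rates, an assumed increase and 40 versus 160 women; precision for the full Section 7.4 population cannot be stated because the number of randomized women is not given. That no interval is planned is a matter of text and needs none of these assumptions. Data collection and the primary analysis are unaffected. The change should be made, but it does not threaten the study.

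**What to change.** Restate secondary hypotheses 1 to 3 in Section 7.3 as estimation aims:

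- **Binary outcomes:** risk difference, outpatient minus inpatient, with a 95% confidence interval.
- **Continuous outcomes:** mean difference with a 95% interval, or the Hodges-Lehmann shift with a 95% interval where Wilcoxon is used.
- **Safety outcomes with no events:** the upper end of the two-sided exact 95% interval for that arm.
- **Interpretation:** state that p > 0.05 will not be read as no difference, that the study is not sized to conclude equivalence or non-inferiority for these outcomes, and that the intervals reflect sampling error only.

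The planned tests can stay beside the intervals. The cost is SAP wording and extra output, with no new data, visits or participants. The price is a more modest safety conclusion.

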## 7.4 Subject Population(s) for Analysis

We will analyze all subjects who were randomized in the randomized control trial design stage of the study, except those who electively withdrew from the trial. We will analyze all subjects enrolled in the prospective stage of the study, who do not electively withdraw.

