A. If the patient is in the outpatient control group, she will arrive to the Family Birth Center at a standard, predetermined time (typically 0730 or 1930) to undergo induction of labor.

B. Method of cervical ripening

1. The only pharmacologic cervical ripening agent to be used is vaginal misoprostol, 25 mcg every 4 hours with a maximum of six doses.
2. She may or may not have a Foley catheter placed as a method of cervical ripening based upon the providing team's discretion.
3. A Foley catheter will be favored during the cervical ripening phase if there is tachysystole and/or a nonreassuring fetal heart tracing precluding further misoprostol administration, provided the Bishop score is still  $<6$ .

C. After cervical ripening is achieved, oxytocin and/or artificial rupture of membranes will be used at the discretion of the providing team.

D. If oxytocin is used during the labor induction, the dose will be increased as determined by the Family Birth Center Oxytocin low dose infusion regimen.

E. The remainder of her care during the first, second, and third stages of labor will be at the discretion of the providing team.

F. All patients' labor progress will be monitored using a partogram. Cesarean delivery will not be performed for arrest of labor or failed induction unless all criteria have been met as outlined by the Family Birth Center Workgroup protocol made effective 6/2/14.

VI. Protocol for the inpatient usual care group (Prospective Study)

A. All methods of cervical ripening and labor augmentation will be at the discretion of the providing team. Cervical ripening will occur as described above with vaginal misoprostol and a Foley catheter; dinoprostone (vaginal prostaglandin, brand name Cervidil) is infrequently used in the Family Birth Center but would now be an option as well. Oxytocin dosing will be increased by the FBC oxytocin low dose infusion regimen, labor will be monitored using a partogram, and Cesarean delivery will continue to be determined by the criteria as described above.

VII. Follow-up

[figure not shown]
A. Inpatient follow-up

1. We will obtain maternal consent to abstract secondary endpoints as described in section 3.3 from the fetal and maternal electronic medical record.

[figure not shown]
B. Follow-up over 6 weeks

1. Secondary endpoints from section 3.3 will be abstracted from the EMR.  

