## **7 Statistical Plan**

### **7.1 Sample Size Determination for Randomized Control Trial**

A power analysis was performed. With 64 patients per arm, we would have 80% power to detect a  $\frac{1}{2}$  standard deviation reduction in the hospitalization time for the outpatient group vs. the inpatient group, assuming a standard deviation of 8 (hours) and a reduction in the mean hospitalization time from 16 to 12 (hours) for the inpatient and outpatient groups, respectively. This also assumes a 2-sided significance level of 0.05.

This is a conservative estimate of the effect of the Foley catheter in the outpatient setting on pre-delivery hospitalization time, our primary outcome. The trial by Sciscione et al. [10]

observed that there was a reduction of 9.6 hours; Henry et al. found a reduction of 11.1 hours [11]. If we replicate this finding, we would be able to detect a difference in the primary outcome with a smaller number of patients, should we not meet desired enrollment.

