### Primary Hypothesis:

We hypothesize that the mean pre-delivery length of stay will be significantly less in the intervention group as compared to the control group. The mean time spent in the hospital between the groups will be compared using a 2-sample t-test or the nonparametric equivalent (Wilcoxon Rank-Sum test).

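### Sections 7.3 and 7.4 do not say whether the randomised (about 1:1) and prospective (1:4) stages are combined; if the single unadjusted test covers both, part of any between-stage difference enters the treatment effect

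*Combined protocol and SAP*

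**What the plan says.** The study began as a randomised trial and, after enrolment proved difficult, became a non-randomised prospective comparison (section 3.1).

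- **Population.** Section 7.4 has one sentence per stage: "We will analyze all subjects who were randomized in the randomized control trial design stage of the study" and "We will analyze all subjects enrolled in the prospective stage of the study". Both leave out elective withdrawals.
- **Primary test.** Section 7.3, Primary Hypothesis: "The mean time spent in the hospital between the groups will be compared using a 2-sample t-test", or the Wilcoxon rank-sum test. Section 7.3 never mentions stage, parity or BMI as terms or strata, and the secondary tests have the same unadjusted form.
- **Allocation.** Section 7.1 sizes the randomised stage: "With 64 patients per arm, we would have 80% power". In the prospective stage (section 3.1, III.B), "Four inpatient comparison control participants will be enrolled with the same parity and BMI strata for every outpatient intervention patient enrolled".
- **Entry and control care.** Also in III.B: "Women who decline participation in the outpatient intervention study may be approached to participate in a limited way as inpatient comparison control participants". The randomised-stage control protocol (section 3.1, V) allowed misoprostol as the only drug for ripening. In the prospective stage (section 3.1, VI) dinoprostone "is infrequently used in the Family Birth Center but would now be an option as well".
- **Counts.** Section 7.2 sizes the prospective study alone: "With 40 subjects in the Foley intervention arm and 160 subjects in the standard of care group". The Study Summary and section 4.3 give the same 200 mothers as the study total.
- **Intention to treat.** Section 4.4.2 applies it to outpatient women who cross over to inpatient care.

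**The concern.** Two populations are named and only one two-group test is given. If that test is run on everyone, randomised women form a larger fraction of the outpatient arm than of the inpatient arm, so arm and stage are associated by design. Any difference in mean stay between stages then leaks into the estimated effect. Such a difference could come from calendar time, or from the change in entry from randomised volunteers to women who chose or declined the outpatient option. Matching on parity and BMI does not prevent this, because those strata do not identify the stage.

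Two further problems do not depend on how large the leak is. A reader could not see how much of the result rests on randomised evidence. The choice between combined and separate analysis is also left open until the data are in hand.

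**Working it through.** **Inputs.** SD 8 h, target reduction 4 h (16 to 12 h) and two-sided 0.05 come from 7.1 and 7.2. The prospective stage is 40 + 160 (7.2) at 1:4 (3.1, III.B). The 1:1 ratio is inferred from 64 per arm in 7.1. Two quantities are assumed because the documents do not give them:

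- k, the number randomised per arm: 5, 10 or 20.
- D, the mean stay in the randomised stage minus that in the prospective stage, taken as equal in both arms: 1, 2 or 4 h in size. D = 4 h equals the whole planned effect and is an upper case.

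**The plan's own figures.** Noncentral t power is 80.1% for 64 v 64 and 80.4% for 40 v 160. Both stated 80% values reproduce.

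**Formula.** The shift in the pooled difference (outpatient minus inpatient) is D × w, where w is the randomised share of the outpatient arm minus the randomised share of the inpatient arm. Positive D hides part of a true reduction and negative D exaggerates it. If D = 0 there is no shift.

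**Case 1: randomised women added to 40/160.** w = k/(40+k) − k/(160+k).

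- k = 5: 5/45 − 5/165 = 0.111 − 0.030 = 0.081
- k = 10: 10/50 − 10/170 = 0.200 − 0.059 = 0.141
- k = 20: 20/60 − 20/180 = 0.333 − 0.111 = 0.222

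**Case 2: 40 is the total number of outpatient women, and the prospective stage keeps 1:4.** There are 40 − k prospective outpatient women and 4(40 − k) prospective controls, so the inpatient arm has 4(40 − k) + k women.

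- k = 5: 5/40 − 5/145 = 0.125 − 0.034 = 0.09
- k = 10: 10/40 − 10/130 = 0.250 − 0.077 = 0.17
- k = 20: 20/40 − 20/100 = 0.500 − 0.200 = 0.30

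**Bias and two-sided type I error of the pooled t-test with no true effect** (noncentral t, SD 8 h):

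| Case | k | Bias at D = 1 / 2 / 4 h | Type I error at D = 1 / 2 / 4 h |
|---|---|---|---|
| 1 | 5 | 0.08 / 0.16 / 0.32 h | 5.0 / 5.2 / 5.7% |
| 1 | 10 | 0.14 / 0.28 / 0.56 h | 5.1 / 5.5 / 7.2% |
| 1 | 20 | 0.22 / 0.44 / 0.89 h | 5.4 / 6.6 / 11.5% |
| 2 | 10 | 0.17 / 0.35 / 0.69 h | 5.2 / 5.7 / 7.6% |
| 2 | 20 | 0.30 / 0.60 / 1.20 h | 5.5 / 6.8 / 12.5% |

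Simulation with within-stage SD 8 h gives slightly lower values at D = 4 h (k = 20: 10.8% in case 1 and 11.6% in case 2), because the stage difference also inflates the estimated variance.

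**Power of the stratified analysis.** An inverse-variance combination of the two stage differences has SE = 8/√(k/2 + n₁n₂/(n₁+n₂)), where n₁ and n₂ are the prospective arm sizes.

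- Case 1: n₁n₂/(n₁+n₂) = 40 × 160/200 = 32. For k = 5, 10, 20 the SE is 8/√34.5 = 1.362, 8/√37 = 1.315 and 8/√42 = 1.234 h, against pooled 1.345, 1.287 and 1.193 h. Power moves from 84.1 to 83.2%, 87.2 to 85.7% and 91.6 to 89.7%.
- Case 2: the term is 0.8 × (40 − k) = 28, 24, 16. The SE is 8/√30.5 = 1.449, 8/√29 = 1.486 and 8/√26 = 1.569 h, against pooled 1.429, 1.446 and 1.497 h. Power moves from 79.5 to 78.4%, 78.5 to 76.3% and 75.6 to 71.6%.

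**The case against.** The strongest reply is that the plan never says it will pool. Section 7.4 describes the stages in separate sentences, 7.1 and 7.2 size them separately, and the title calls the study a non-randomised prospective one. This stands. A reader might infer that 7.3 and 7.4 commit to a naive pooled test and that the result is therefore biased. The documents support only an open question, with a bias that follows under one of two possible readings.

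The size also deserves restraint. Difficulty enrolling suggests that k was small. Site, eligibility and the intervention protocol are shared across stages, and dinoprostone is described as uncommon. Material inflation needs k near 20 together with D near the whole planned effect, and nothing in the documents supports either.

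A reader might also hold both 40 and 160 fixed with the randomised women inside them, which gives a share of 20/40 − 20/160 = 0.375 at k = 20. That leaves 20 prospective outpatient women and 140 prospective controls, or 1:7, which contradicts the four-to-one enrolment in section 3.1. Case 2 keeps 1:4 and is the version the documents allow.

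Finally, stage adjustment leaves the larger threat untouched: women who declined the outpatient option may serve as controls. That is true, and it limits what the fix can claim. It does not make the stage term unnecessary.

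**Conclusion.** The point holds in conditional form. The plan does not say whether the two stages are combined, its only primary test has no stage term or strata, and it is unclear whether the randomised women are within the 40 + 160. If the test covers both stages, between 0.08 and 0.22 of any between-stage difference enters the effect for k = 5 to 20 in the added case, and 0.09 to 0.30 if the randomised women are counted among the 40. At k = 5 to 10 and D = 1 to 2 h in the added case, that is 0.08 to 0.28 h, with type I error of 5.0 to 5.5%. The upper case in that setting, k = 20 with D = 4 h, gives 0.89 h and about 11%.

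The bias is probably small and its direction is unknown. All figures rest on assumed k and D, SD 8 h and the same stage shift in both arms. They do not cover a stage-by-treatment difference, which the change in control care could produce. The change should be made because it is cheap and because the reporting gap exists whatever k and D turn out to be.

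**What to change.** In 7.3 and 7.4:

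1. State whether the stages are combined for the primary analysis.
2. Make any combined analysis stratified by or adjusted for stage and the recorded parity/BMI strata: a linear model with arm, stage and strata, or the van Elteren test if the rank test is used.
3. Report each stage's mean difference with a 95% confidence interval, analysing the randomised stage by allocated arm in line with 4.4.2.
4. State whether 40 + 160 includes the randomised women, and align 7.2, the Study Summary and 4.3.
5. Say in the report that a stage term removes neither self-selection within the prospective stage nor a stage-by-treatment difference from the changed control care.

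The cost is SAP wording, stage and strata terms in the model, and one table, from data the study already collects. Stratifying by stage loses about 1 to 2 points of power if the randomised women are added to 40/160, or about 1 to 4 points if they are counted within the 40 outpatient women at 1:4. The randomised-stage estimate will be imprecise: the 95% half-width, t × 8 × √(2/k) with 2k − 2 degrees of freedom, is about 11.7, 7.5 or 5.1 h at k = 5, 10 or 20.

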#### **4.3 Subject Recruitment, Enrollment and Screening**

We anticipate a targeted population of 400, which includes 200 mothers and their 200 infants. Data will be collected from these 400 charts after delivery.

We anticipate that 250 women in total will provide informed consent before giving birth to their babies. That is, we estimate that 50 women who are initially consented for the study will become ineligible for inclusion in the trial, for example due to spontaneous onset of labor, prior to induction of labor. These women will be considered screen failures.

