Finally, the pregnant woman may become excluded from study shortly after arrival to the Family Birth Center for initiation of the planned induction of labor. Any of the above-listed reasons (vaginal bleeding, spontaneous labor, premature rupture of membranes, etc) diagnosed at presentation will be reason to exclude the woman from participation. Furthermore, *after* Foley catheter placement, a patient may be excluded from the trial should any of the following occur:

1. She is diagnosed with a condition that requires immediate admission for induction of labor (such as gestational hypertension or preeclampsia)
2. She develops vaginal bleeding more than spotting that is clinically concerning for placental abruption
3. She spontaneously labors
4. She undergoes premature rupture of membranes
5. The post-placement fetal heart tracing is non reassuring such that outpatient management is not recommended
6. She develops a fever and/or chorioamnionitis

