#### **4.4.2 Data Collection and Follow-up for Withdrawn Subjects**

Data will not be collected from women who electively withdraw from the study. Data will be collected on all women who are randomized to a treatment group. Should patients from the outpatient group cross over to the inpatient group (i.e. if they meet exclusion criteria), analysis will be by intention to treat.

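### Sections 4.3 and 4.4.1 remove women who become ineligible before ripening starts, sections 4.4.2 and 7.4 appear to keep them, and with no common starting point the choice would act unequally on the two groups

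*Combined protocol and SAP*

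**What the plan says.** **Text that removes these women.** Section 4.3 aims for data on 200 mothers and their 200 infants and expects 250 women to consent: "we estimate that 50 women who are initially consented for the study will become ineligible for inclusion in the trial". It gives spontaneous labour as an example and calls these women screen failures. Section 4.4.1 lists labour, pre-labour rupture of membranes, new diagnoses, fever and other events between the clinic visit and induction as grounds for exclusion. It then says that the same findings "diagnosed at presentation will be reason to exclude the woman from participation".

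**Text that keeps them.** Section 7.4: "We will analyze all subjects enrolled in the prospective stage of the study, who do not electively withdraw". Elective withdrawal is the only route out. Section 4.4.2 says that if outpatient women "cross over to the inpatient group (i.e. if they meet exclusion criteria), analysis will be by intention to treat".

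**When each group joins.** Under section 3.1 III.A, outpatient women are met and consented at a clinic appointment. Section 3.1 III.B gives two sources of controls. One is women who decline the outpatient intervention. The other is found when the coordinator checks the unit's board: "screen the OB White Board daily in the Family Birth Center to identify patients presenting for induction of labor". In both parts consent is the last enrolment step described, and no separate point of enrolment is defined.

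**The concern.** Consider an outpatient participant who consented in clinic.

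- **She labours before the induction day.** Section 4.3 leaves her out. Section 7.4 keeps her if *enrolled* means consented.
- **She arrives for induction and is found ineligible before a Foley is placed.** Section 4.4.1 excludes her, while section 4.4.2 analyses her in the outpatient group. Here the two sections conflict directly.

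The study is unblinded (section 5.8), so an analysis set left open would be settled by people who can see the outcomes.

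The choice is also not neutral between groups. Outpatient women, and decliner controls if they consent in clinic, pass through an interval between consent and induction in which these events can occur. White Board controls have already come through that interval when they are identified. Keeping the losses would therefore add women who never had outpatient ripening mainly to the outpatient group. The planned primary test is an unadjusted two-sample comparison, and matching is on parity and body mass index only, so nothing in the plan corrects for this.

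**Working it through.** **Inputs from the documents.** Section 7.2: "A power analysis was performed and assumed a standard deviation of 8 hours"; 40 outpatient and 160 standard-care women; 16 h against 12 h; two-sided 0.05. Section 4.3: 50 of 250 consented women lost, 50/250 = 20%. The split of the 50 by group is not given.

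**Assumptions.** The loss rate of 20% applied to outpatient women (40 remaining + 10 lost = 50), the mean stay *m* of the lost women, and the mix of control sources.

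**1. The plan's own figure.** Standard error = 8 × √(1/40 + 1/160) = 1.41 h. 4/1.41 = 2.83, which on the noncentral t with 198 degrees of freedom gives power of 80.4%. The stated 80% reproduces. It takes 40 and 160 as the numbers analysed, which fits the 200 mothers in section 4.3.

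**2. Shift with no true effect.** Difference (outpatient minus inpatient) = *f*ₒ × (*m* − 16) − *f*c × (*m* − 16), where *f*ₒ and *f*c are the shares of lost women among those analysed in each group. Outpatient: *f*ₒ = 10/50 = 0.20. Controls: *f*c = 0 if all come from the White Board. If half are decliners with the same loss, 80 decliners remain and 20 more are lost but analysed, so *f*c = 20/180 = 0.111.

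The last column comes from 20,000 simulated trials per row (Welch test, SD 8 h). It gives the chance of a significant result favouring outpatient care, nominally 2.5%.

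| Lost women's mean | Controls | Difference | False favourable result |
|---|---|---|---|
| 8 h | all White Board | 0.20 × (−8) = −1.6 h | 20% |
| 10 h | all White Board | 0.20 × (−6) = −1.2 h | 13% |
| 12 h | all White Board | 0.20 × (−4) = −0.8 h | 8% |
| 8 h | half decliners | (0.20 − 0.111) × (−8) = −0.7 h | 6% |
| half 8 h, half 16 h | all White Board | 0.20 × (−4) = −0.8 h | 8% |
| half 8 h, half 16 h | half decliners | (0.20 − 0.111) × (−4) = −0.4 h | 4% |
| 20 h | all White Board | 0.20 × (+4) = +0.8 h | below 2.5% |

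If all controls were decliners with equal loss, *f*ₒ = *f*c and the shift would be zero.

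**3. Dilution with a true 4 h effect.** If the lost women have the inpatient mean of 16 h, the difference is 0.80 × 4 = 3.2 h. With 50 and 160 analysed, the standard error is 8 × √(1/50 + 1/160) = 1.30 h and 3.2/1.30 = 2.47, giving power of 69%.

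**The case against.** The strongest reply is that section 4.3 already settles losses before arrival. It calls these women screen failures and plans chart data only for the 200 mothers and their infants, and section 7.2 is powered on the same 200. On that view *enrolled* in section 7.4 means those 200, and the two sections agree. Section 4.4.2 speaks partly of randomized women, and its intention-to-treat sentence concerns women who cross over. A woman who labours days before induction has not crossed over from anything.

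Much of this stands. For losses before arrival, the better reading is exclusion, and section 7.4 conflicts only if taken literally. But no section defines *enrolled*, and section 3.1 III describes enrolment as ending in consent. The reply also leaves open the outpatient woman found ineligible on arrival, whom section 4.4.1 excludes and section 4.4.2 analyses.

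A reader might go further and infer that no control can have these events, or that the plan carries a 20% false-positive risk. The documents support neither:

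- White Board women are one of two control sources. Decliners may consent before induction day and face the same interval.
- The 20% needs every control to come from the White Board and an 8 h mean for the lost women, which no section gives.
- The reasons in section 4.4.1 include preeclampsia, growth restriction and contraindications to vaginal delivery, so short stays cannot be presumed.

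**Conclusion.** The concern holds as an unresolved definition of the primary analysis set, with unequal consequences for the groups. The conflict is direct for outpatient women found ineligible on arrival before Foley placement. For losses before arrival it depends on reading section 7.4 literally.

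Neither the size nor the direction of the bias is known from the documents. Under the assumptions shown, the shift with no true effect runs from about −1.6 h, which is 40% of the 4 h target, through −0.4 h to +0.8 h. The chance of a false favourable result is 20% at the first of these and 4% at the second. Where there is no bias because the lost women resemble inpatients, the cost is power: about 69% instead of 80%. All these figures assume that 10 of 50 outpatient women are lost but analysed. The sample-size arithmetic itself is sound. The ambiguity should be removed before analysis.

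**What to change.** 1. In section 7.4, define the prospective-stage analysis set in both groups as women who present for the scheduled induction and are eligible at the arrival assessment, before any ripening method. Classify them by intended pathway at that moment.
2. State that women lost before that point are counted by group and reason but not analysed, in line with section 4.3.
3. Limit the intention-to-treat sentence in section 4.4.2 to events after that point, and reconcile it with the on-arrival and post-placement exclusions in section 4.4.1.
4. Apply the four-to-one matching in section 3.1 III.B.3 to outpatient women in this set, so that controls are not matched to women who never reach induction.
5. Base the common eligibility rule on criteria assessed in both groups. Section 6.2 lists the amniotic fluid index for all patients but notes that it is not routine in usual care. The rule should not depend on a measurement made in only one group.

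The cost is wording in sections 3.1, 4.3, 4.4 and 7.4 and a table of losses by group. With item 5 observed, no extra patients or procedures are needed. The downside is that some consented women are not analysed, which section 4.3 already expects.
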